To generate willingness to pay (WTP) estimates and assess how LPG purchases vary with price, we will follow a method used in other economic studies of health-related technologies, known as a (modified) Becker-Degroot-Marshack (BDM) mechanism (Becker et al. 1964; Levine et al. 2012; Guiteras et al. 2014). In the first stage, a participant indicates her WTP (i.e., submits *bids*) for a set of different potential LPG stove packages. In the second stage, the researcher randomly draws one stove package, along with a random *offer price* for that package. If the bid amount is greater than the offer price, the participant has the option to purchase the stove package at the offer price. If the offer price exceeds the bid, the participant does not purchase the stove. Economic theory suggests that this procedure incentivizes participants to indicate their true WTP. The method also maximizes the statistical power of the study, by capturing more variation in WTP than alternative approaches.

In addition, a post-purchase marketing intervention will be randomly assigned to half of study participants that buy stoves. Many prior studies, and our own work, have shown that even households that have LPG stoves usually continue to use traditional stoves alongside their cleaner stoves. Households assigned to the post-purchase marketing arm will receive text messages and in-person visits encouraging them to use their LPG stoves more and their charcoal and wood stoves less. We will analyze whether these treatments influence stove use rates (measured through surveys and stove use monitors) and perceptions of the stoves (measured through the endline survey).

Project Timeline

The proposed research will take place over a three year period, with activities in each year indicated in Table 2. Table 2: Timeline of project activities

PROJECT WORKPLAN												
		Yea	ar 1			Yea	ar 2			Ye	ar 3	
	Sep	t 2015	-Aug 2	2016	Sept 2016-Aug 2017			Sept 2017-Aug 2018				
	Q1	Q2	Q3	Q4	Q1	Q2	Q3	Q4	Q1	Q2	Q3	Q4
Preparation, including IRB approvals												
Survey Development and												
Intervention Planning												
LPG Supply Survey												
Household Surveys												
P3 Bio Intervention												
- Stove meetings, offers made, orders												
- Stoves delivered, payments												
collected												
P3 Gas Intervention												
- Stove meetings, offers made, orders												
- Stoves delivered, payments												
collected												

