costs about \$80. REACCTING results, pretesting and focus group activities in the study area will be used to determine appropriate price points / discount levels for the study design such that we would expect to see variation in price across the different experimental price groups. In the urban sub-sample, the P3 Gas participants will be shown the components of the LPG stove and fuel packages (see Figure 6).

For the P3 Bio study, participants will select stoves at the conclusion of their small group meeting. At the prices assigned to each cluster, participants can elect to purchase a total of 0, 1, or 2 stoves, of either type (Greenway or Jumbo). Participants will be informed that the project team must order stoves from their manufacturers and that the stoves will take 2-3 months to arrive in Ghana after the orders are made. TOnce participants have made their selection, they will sign or thumbprint an agreement that specifies the types of stoves they have agreed to purchase, the purchase price, and the payment schedule.

For the P3 Gas intervention, stove offers will be made using a (modified) Becker-Degroot-Marshack (BDM) mechanism (Becker et al. 1964; Levine et al. 2012; Guiteras et al. 2014). Project staff will visit each participant in their homes, following the group information meeting, and conduct the following procedure. First, the auction mechanism is explained to the participant, and two practice rounds are conducted using small token items (soap, small bags of rice). Next, the stove auction proceeds in two stages. In the first stage, the participant indicates her WTP (i.e., submits *bids*) for each of the 6 LPG stove packages (Figure 6). She may elect NOT to bid on any package for which she has no interest. In the second stage, the researcher randomly draws one stove package from the set of packages the participant chose to bid on, along with a random *offer price* for that package. If the bid for that package is greater than the offer price, the participant must purchase the stove package at the offer price. If the offer price exceeds the bid, the participant does not purchase the package. If the participant wins the auction, she will sign an agreement stating which package she will receive, the amount to be paid, and the payment schedule.

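### P3 Gas auction: because the package is drawn only from those a participant bid on, one with a clear favourite gains by leaving the others blank, so blanks cannot be read as lack of interest

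*Combined protocol and SAP*

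**What the plan says.** Section XII (Procedures) asks each participant to bid on the six LPG packages of Figure 6, with an opt-out: "She may elect NOT to bid on any package for which she has no interest". The draw follows: "the researcher randomly draws one stove package from the set of packages the participant chose to bid on", together with a random offer price. The purchase rule is binding: "If the bid for that package is greater than the offer price, the participant must purchase the stove package at the offer price". She knows the rules in advance: "First, the auction mechanism is explained to the participant", and two practice rounds with small items precede the real one.

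Section IV (Component #2, Activity 2.1) describes the same auction differently. There, "the researcher randomly draws one stove package, along with a random" offer price, with no mention of a restriction to packages that received a bid. On a winning bid, "the participant has the option to purchase the stove package at the offer price". The same paragraph states the property on which the method relies: "Economic theory suggests that this procedure incentivizes participants to indicate their true WTP".

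The text supplied gives no rule for analysing packages without a bid.

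**The concern.** The usual argument for this kind of auction is that a bid cannot influence the price paid, so nothing is gained by misstating it. That argument covers the amount bid on a package already in the draw. It does not cover the choice of which packages enter the draw, and section XII leaves that choice to the participant. Each extra package she lists lowers the chance that her favourite is drawn.

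Three things follow. A blank may mean that she wanted a better chance at another package, whereas section XII presents it as lack of interest. WTP for the less preferred packages is then missing for reasons tied to WTP itself. And the package a household ends up with is partly self-selected, which matters for any later comparison across packages. Figure 6 varies the stove and home delivery, so contrasts between packages are the natural use of six bids per household, although the plan does not spell out such an analysis.

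**Working it through.** **Inputs from the plan.** Six packages with market values GHC 550, 550, 500, 500, 450 and 450 (Figure 6; each equal-valued pair appears to differ only in home delivery); 300 households (section VI); the draw and purchase rules of section XII. Table 1 covers P3 Bio only, so there is no P3 Gas figure to reproduce.

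**Assumed.** The plan gives neither an offer-price nor a WTP distribution. All GHC results below rest on assumed ones.

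**Step 1: the amount bid.** Let v be her WTP for the drawn package and P the random offer price. A bid b yields E[(v − P) · 1(P < b)]. Raising b above v adds only purchases at a loss; lowering it gives up gainful ones. The best bid is b = v. A grid check with v = 300 and offers uniform on 0 to 550 returns 300. Amounts on included packages stay truthful.

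**Step 2: the set bid on.** Let E_k = E[(v_k − P_k)+] be the expected surplus on package k. Under section XII, truthful bidding on a set S is worth

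(1/|S|) × Σ E_k over k in S.

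This is an average and cannot exceed its largest term. It equals that term only if every package in S ties for best. With a unique best package, the optimal set is that package alone. The same holds with expected utility in place of surplus.

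**Step 3: size.** For offers uniform on 0 to h and v ≤ h, E = v²/(2h).

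| Assumed WTP (GHC) | Assumed offers | E_k for the six packages | All six | Best only | Gain |
|---|---|---|---|---|---|
| Half of market value | 0 to market value | 68.75, 68.75, 62.5, 62.5, 56.25, 56.25 | 62.5 | 68.75 | 10% |
| Half of market value, plus 20 for delivery | 0 to market value | 79.1, 68.8, 72.9, 62.5, 66.7, 56.2 | 67.7 | 79.1 | 17% |
| 300 down to 250 in steps of 10 | 0 to 450 | 100 falling to 69.4 | 84.4 | 100 | 19% |
| 300, 260, 240, 200, 180, 140 | 0 to 450 | 100, 75.1, 64, 44.4, 36, 21.8 | 56.9 | 100 | 76% |

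In the first row packages 1 and 2 tie, so bidding on either or both is equally good; the other four are still left out.

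The second row was extended to WTP at 30%, 50% and 70% of market value (plus 20 for delivery) and to three offer distributions: uniform from 0 to market value, from 0 to 550, and from 0.2 to 0.8 of market value. All 63 non-empty sets were listed in each of the nine cases. A single package was best every time, with gains from 15% to 38%.

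**Step 4: what the bids would show if everyone acted on this.** In nine simulated scenarios of 20,000 households each (WTP centred on half of market value, varying by household and stove, with a non-negative value for delivery), a single package was best for every household. The median gain ran from 20% to 86%. Mean WTP among those bidding on package 1 was 301 to 366, against a true mean of about 299; for package 5 it was 233 to 319, against about 249. Each bid is truthful, but the bidders are a selected group. Packages 2, 4 and 6 received no bids, because delivery had positive value and paired packages shared an offer distribution.

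**Step 5: draw from all six.** The value becomes (1/6) × Σ E_k over the packages bid on, so each truthful bid adds a non-negative amount. In the second row of the table, bidding on all six is worth 67.7 and bidding on one is worth 79.1/6 = 13.2. Bidding on all six was best in all nine cases of step 3.

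**The case against.** The strongest reply has four parts.

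*The instructions ask for bids on all six packages.* Section XII allows a skip only for lack of interest, and section VIII has staff stress honest statements of WTP. A strategic blank departs from that. This is fair, but nothing verifies interest, and the draw rule rewards omission.

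*The bids themselves remain sound.* This stands. A reader might infer that every recorded WTP is distorted. Step 1 shows that it is not, given the binding purchase rule of section XII.

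*The result is not universal and its size is not established.* This also stands. Offer prices may differ by package, and if expected surplus is equal across packages, bidding on all six is just as good. The favourite is the package with the highest expected surplus, which matched the highest WTP for only 61% to 100% of simulated households. The 76% comes from WTPs with more than a twofold spread, while market values run only from 450 to 550. One might also infer that the component will yield 300 bids in place of 300 × 6 = 1,800, or that the value of delivery cannot be estimated. Both are the extreme in which every participant exploits the rule, and the documents give no evidence on how many would.

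*The stated aims largely survive.* Section IV speaks of WTP estimates and of how purchases vary with price. The offer price is still random, the package is random given the bid set, and the post-purchase marketing comparison is randomised among buyers. That is right for those analyses. It does not rescue WTP across the six packages, or comparisons that treat the package as randomly assigned to everyone.

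**Conclusion.** The concern holds, within limits. Under the section XII draw rule, a participant with a unique best package gains by leaving the others blank, and nothing elsewhere in the documents removes that incentive. The true-WTP statement in section IV therefore does not extend to the full six-package set. Bid amounts on included packages keep their truthful incentive.

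The direction follows from the rule and needs only that one package be strictly best for her in expectation. The size rests on assumed distributions: about 10% to 76% in the worked examples, with simulated medians up to 86%. How much bias would reach the data depends on how many participants act on the incentive, which the documents do not show.

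Sections IV and XII also differ on two matters of fact. Section IV does not state the restriction on the draw, although it does not say that all six packages are always in it either. And one section makes purchase optional where the other makes it obligatory. The second difference bears on this point: if a winner could decline, bidding above her WTP would cost her nothing, so step 1 would no longer favour the truthful amount strictly.

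**What to change.** In section XII and the field script, draw the package from all six for every participant, treat a drawn package without a bid as no purchase, and explain this before bidding starts. Package assignment can then be analysed as random across all six. Reword section IV so that both sections give the same draw set, and reconcile the two statements on whether a winning bidder may or must buy.

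The change to the draw is one sentence in the procedure and script. Its price is that some draws end without a sale: if four of six packages receive bids, 2/6, or about 1 in 3, land on a package without one. That leaves somewhat fewer buyers for the post-purchase marketing comparison. The loss should be limited, because the change also removes the reason to leave blanks.

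If bids have already been collected under the current rule, keep each participant's bid set in the data, treat package assignment as random only within that set, and do not read blanks as zero or low WTP.

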For this activity, we will begin by using existing data on household locations, cooking practices, and detailed socioeconomic indicators from the NHRC's district-wide demographic surveillance survey (DSS) to analyze how LPG use varies spatially and according to household characteristics (e.g., education, socioeconomic status). This analysis will also include information collected in Activity 1.1 to assess how LPG use is related to distance from LPG supply centers. The DSS data will be managed by the NHRC team, following the institution's guidelines for management of this dataset. The NHRC collects the DSS data for the purposes of understanding population characteristics and trends over time, such that the analyses conducted as part of this project fall within the purposes outlined when the data was originally collected. Furthermore, the analyses conducted for this study will not use identifiable information about participants.

We will also use the DSS data to randomly sample of 300 households in the district, stratified to represent LPG users and non-users in urban and peri-urban areas. These households will complete the same baseline survey as the rural P3 Bio households, which will include modules that measure current

cooking practices, including stove and fuel stacking (i.e., use of multiple types of stoves and/or fuels), as well as perceived barriers to LPG adoption, including price, savings/credit constraints, access/availability, and other perceptions (e.g., safety concerns).

Phase 2: Experimental Interventions to Increase LPG Adoption

Activity 2.1: Intervention Development and Implementation. Purpose: To design and implement a set of supply- and demand-focused interventions intended to increase LPG adoption in the K-N.

All of the 300 urban and peri-urban households surveyed in Activity 1.2 will be enrolled in the Phase 2 interventions, in which different stove-fuel packages will be offered. The packages that will be offered are shown in Figure 6.

Packaga Componentes				Package I	Numbers:		
Package Components:	Package components:		2	3	4	5	6
	2 Burner Stove	✓	✓				
	1 Burner Local Stove			×	×		
- Coo	15 kg cylinder + regulator + hose (recirculation)	~	~	1	1	~	~
	4 Fuel Refill Vouchers	\checkmark	\checkmark	✓	✓	\checkmark	\checkmark
	Home Delivery	✓		√		✓	
	Market value:						
	GHC	550	550	500	500	450	450
	USD	\$140	\$140	\$125	\$125	\$110	\$110

Figure 6: LPG stove packages

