We are requesting a waiver of documentation of informed consent. This research poses no more than minimal risk of harm to subjects and involves no procedures for which written consent is normally required outside of the research context.

XII. PROCEDURES

Household-level Interventions and Data Collection (P3 Bio and P3 Gas)

The study's data collection instruments are summarized in Table 4, and the list of procedures, visits, and time constraints are listed in Table 5.

Several data collection methods will be used to measure key outcomes of interest.

- Household surveys: A baseline survey will measure household composition and demographics, attitudes and priorities, cooking behaviors (including type(s) of stoves used, fuel use, foods cooked, who cooks within household), knowledge and perceptions of issues related to cooking practices, demand for new stoves, and self-reported health measures. One short follow up survey will cover households' stove perceptions. A full survey, covering the same questions as the baseline survey, will be repeated at the end of the study.
- 2) Stove use monitors: In a subset of study households, stove use monitoring equipment will be attached to all stoves in the household (including traditional/old stoves and stoves distributed as part of the study intervention). These monitors will provide measurements of stove temperature every 5 minutes in order to indicate when each stove is in use over a given period. Study personnel will visit homes every 3 months to make sure these monitors are intact and working and to download data from the monitors.

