XIX. PROVISIONS TO MONITOR THE DATA FOR THE SAFETY OF PARTICIPANTS

Where possible, interim analyses of personal exposure will be conducted to check whether exposure to pollutants significantly increases in groups with different types of new stoves. If this is found to be the case, this information will be provided to participants and households will have the option to return their new stoves (and receive refunds in cases where stoves were purchased). Other adverse events (e.g., broken stoves) will be reported to [name] (NHRC) for appropriate follow-up and management.

XX. PROVISIONS TO PROTECT THE PRIVACY INTERESTS OF PARTICIPANTS

Data collection will occur only in contexts in which the subject is aware of and approves of the activity. Household surveys will occur in or near respondents' homes only when and if respondents have agreed to be surveyed. Similarly, respondents will be informed of and will consent to use of stove use monitors, personal exposure monitors, and cameras prior to any data collection using these instruments.

XXI. MEDICAL CARE AND COMPENSATION FOR INJURY

> Not applicable.

XXII. COST TO PARTICIPANTS

Households' use of the new stoves requires use of fuel (mainly wood or biofuel); however, these are fuels that the household would be using in the absence of our study, and in theory the new stoves will use less fuel than households' existing stoves.

P3 Bio households will be offered stoves at a positive price. In order to receive stoves, households will have to pay for them. However, households will not be required to purchase stoves. Every attempt will be made to make it clear to participants that purchasing stoves is completely voluntary.

P3 Gas households are being offered stove – fuel packages, and will have the option of purchasing these packages, which will incur costs. However, these packages will be subsidized relative to their market value, and the bidding mechanism should ensure that no participants will pay more than they are willing and able for these products.

XXIII. DRUG ADMINISTRATION

> Not applicable.

XXIV. INVESTIGATIONAL DEVICES

> Not applicable.

XXV. MULTI-SITE STUDIES

This study is being conducted through a collaboration among CU-Anschutz, CU-Boulder, North Carolina State University (NCSU), and the Navrongo Health Research Centre (NHRC).

Institutional roles are outlined in Table 7.

Institution	Key Personnel	Role

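### Fire, burns and LPG explosion are named as stove risks, but no described instrument asks households that received a stove whether one occurred

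*Combined protocol and SAP*

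**What the plan says.** Section XVI lists fire as a hazard of all the stoves and explosion as a hazard of misused LPG. Section XVII adds burns. The answers in Section XVII are mainly preventive: user training for biomass stoves; for LPG, safety education at several points, cylinder exchange with leak checks at the refilling station, and visits to inspect stoves.

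Section XIX (safety monitoring) has two parts. The active part concerns pollutants: "Where possible, interim analyses of personal exposure will be conducted to check whether exposure to pollutants significantly increases" in groups with different new stoves. The offer to take a stove back, with a refund if it was bought, follows from that result. The second part reads "Other adverse events (e.g., broken stoves) will be reported to" the NHRC contact "for appropriate follow-up and management". A recipient and a response are therefore stated.

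Section XII describes the surveys by topic. The baseline covers demographics, cooking behaviour, perceptions, stove demand and self-reported health. For the interim round, "One short follow up survey will cover" stove perceptions. For the endline, "A full survey, covering the same questions as the baseline survey, will be repeated at the end of the study". Table 4 adds health symptoms and health expenditures to the survey topics.

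**The concern.** The project supplies the stoves and, in one arm, sends LPG buyers "text messages and in-person visits encouraging them to use their LPG stoves more". It names accidents with those stoves as a risk but describes no step at which a household that received one is asked about them. If the text is followed as written, reporting depends on a household volunteering an incident or on staff noticing one.

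Two things are at stake. A household that has had a burn or a gas leak may not reach the follow-up that Section XIX promises. And if few or no incidents are on record at the end, that record cannot separate safe use from incidents nobody asked about. No later analysis can recover what was not collected.

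**Working it through.** No arithmetic applies: the plan states no incident rate, target or count for these events. The check is to take each described contact after stove delivery and ask whether the text says it records fires, burns, leaks or explosions.

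**Surveys**
- *Short follow-up (Section XII):* described as covering stove perceptions. No incident topic.
- *Endline (Section XII):* repeats the baseline. Table 5 places the baseline at Visit 1 and stove selection at Visit 2, and delivery comes later still. The described content therefore gives no reason to expect a question on incidents with a study stove.
- *Health items (Section XII, Table 4):* a burn might be mentioned, but nothing described would link it to a study stove.
- *LPG barriers module (Section IV, Activity 1.2):* includes safety concerns. It measures a perception, not whether something happened.

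**Instruments**
- *Stove temperature, personal exposure and camera monitoring (Section XII):* these measure use, pollutants and proximity. Stove monitoring is limited to a subset; there, "Study personnel will visit homes every 3 months" to check equipment and download data. Incident questions are not mentioned.

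**Other contacts**
- *LPG inspection visits and cylinder leak checks (Section XVII):* the closest to safety surveillance. They check equipment and practice; recording past incidents is not described. No equivalent inspection is described for biomass stoves.
- *Marketing visits (Section IV, Activity 2.1):* assigned to half of the participants who buy LPG stoves, with the purpose of encouraging use.
- *Payment collection (Section XII, Table 2):* first payment at delivery, the rest within six months. It gives further contact with buyers on instalments, but not with anyone given a stove free.
- *Contact details (Section X):* given to every participant. This is a passive route with no stated instruction to report stove incidents.

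**Safety provisions**
- *Section XVII, monitoring data and amending the design:* placed under the risk that exposure worsens, so it does not cover accidents.
- *Section XVII, contact protocol for malfunctions:* placed under stove use monitoring, so it concerns monitoring equipment. No matching protocol is described for the stoves.
- *Section XIX, other adverse events:* names the recipient. It does not say who reports, how events are elicited, or when.

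Several of these contacts could bring an incident to light. None is described as asking about one or recording it.

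**The case against.** The strongest objection is that absence is being read from topic-level summaries. No survey topic is itemised, so the lack of a line on burns says little, and the health, perception or safety-concern topics could contain such an item. The questionnaires and the consent statement are not available and might settle the matter. This stands, and it limits the point to what the text describes. A reader might infer that households are never asked about accidents, or that the study has no route for injuries. The documents do not support either: the first cannot be known, and Section XIX does name a recipient and a response.

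Second, the gravest hazard, LPG explosion, already has education, training at delivery, inspections and leak checks. That is fair as prevention and partial detection. It does not amount to asking about events, and biomass recipients have no described inspection.

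Third, no injury count is planned and injury incidence is not a study aim, so no planned result is misled. That also stands, and it is why the point is optional. The participant-safety reason remains: an event has to be known before it can be followed up.

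Fourth, asking recipients about burns and explosions could colour their answers on perceptions and use, which are key outcomes, and would do so only among recipients. This is a real cost, and it determines where the item should go.

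**Conclusion.** The point holds for the available text: the named accident risks have no described means of elicitation, while pollutant exposure has a planned analysis. It rests on the surveys following their descriptions in Section XII and Table 4, and would fall away if the questionnaires already contain an incident item.

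No numerical size can be given. The documents state neither an incident rate nor how many households will receive each stove, and Table 1's adoption rates are power-calculation scenarios, not forecasts. A reader might infer that incidents will be missed at some appreciable rate, or that the study's findings are compromised. Neither follows: nothing in the documents gives a rate, and the adoption, use and perception estimates do not depend on incident recording. This is a cheap, optional participant-safety improvement.

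**What to change.** For every household that has received a study stove, add one fixed item: any burn, fire, gas leak, explosion or other injury linked to a study stove since delivery or since the last survey, and which stove.

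- **Where:** at the end of each follow-up survey held after delivery and of the endline, after all perception and use questions. Ask it at the planned LPG inspection visits as well. Section XII's text plans one follow-up survey and Table 5 lists two, with no timing relative to delivery, so the sponsor should state which of them qualify.
- **Action:** send positive answers promptly to the existing NHRC contact.
- **Reporting:** descriptive counts by technology (LPG, Greenway, ACE), with the number of households asked.

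The cost is one item on contacts already planned and one descriptive table. The downsides are slightly longer surveys, imperfect recall, and a small risk of priming perception and use answers in later rounds, which placing the item last reduces but does not remove. The item supplements the present reporting route. It is not real-time surveillance, and it would not show whether accident risk rose or fell relative to traditional stoves.
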